### 347 **Chapter 4 Randomization**

348 Participants will receive the two different experimental conditions (NAP and UMPC) in random  
349 order. Once eligibility is met and screening procedures are completed, the participant may continue  
350 to randomization. Screening failures and dropout participants may be replaced.

## 351 **Chapter 5 Pre-Hotel Schedule**

### 352 **Visit 2 and 4**

#### 353 **5.1 Pre-Hotel Check-In**

354 Participants will be contacted by the study team approximately 1-3 days prior to each hotel session  
355 if most recent contact with the study participant exceeds 10 days. The study team will verify the  
356 following information:

- 357 • Inquire about any changes to the participant's medical history
- 358 • Remind the participants to place a new sensor for proper warm-up prior to session
- 359 • Verify with the subject that the goal CGM reading at time of arrival is between 80-250  
360 mg/dL; this may require contact with the study physician prior to arrival on the day of  
361 the study visit
- 362 • Should any concerns regarding medical history, pump information, or unforeseen  
363 issues arise, the session will be cancelled for that participant at the discretion of the  
364 investigator.

#### 365 **5.2 Other Issues**

366 Data-driven optimization of pump settings can occur any time prior to the hotel sessions,  
367 particularly if the participant contacts the study physician due to concerns about their pump  
368 settings due to recurring hypo- or hyperglycemia. No pump settings changes can occur during  
369 NAP or UMPC algorithm testing.

# CLINICAL PROTOCOL

## 370 **Chapter 6 Hotel Session**

### 371 **Visit 3 and 5**

372 Each participant will have two hotel sessions. Each session will be of approximately 20 hours  
373 duration (see Figure 1). The sessions may occur sequentially within the same hotel stay or within  
374 28 days of each other. If the hotel sessions are sequential, it is not required that the initial hotel  
375 check-procedures procedures be repeated.

### 376 **6.1 Qualifications and Role of the Staff**

377 There will be at least two study staff present at all times at the study site, at least one of whom will  
378 be clinical (e.g. nurse, physician, nurse practitioner, physician assistant). There will be a physician  
379 at the hotel or nearby on call during the study. In addition, at least one engineer will be on call  
380 during the entire session. Participants will be remotely monitored by at least one study team  
381 member using a web-based remote monitoring system that has been previously established for  
382 DiAs. The web-based remote monitoring system will display real-time insulin delivery, CGM and  
383 other system information to allow for patient safety monitoring. Study team members will be  
384 trained in all protocol and glycemic treatment guideline procedures.

385 The study team will be responsible for monitoring and managing the study insulin pump during  
386 the hotel sessions. The participants may be provided a quick overview on its functionality to  
387 understand the equipment. The study team will assist the participant in study pump infusion site  
388 initiation and will start the participant on the study pump. The study pump will be programmed  
389 with the participant's usual basal rates and pump parameters.

390 The participant will be instructed on charging the pump, navigation through menus, bolus  
391 procedures including stopping a bolus, etc. The participant will be instructed to notify study staff  
392 if they experience any issues with the study devices during the hotel session. If insulin is delivered  
393 by any means other than the study pump (e.g. injection of subcutaneous insulin via syringe in the  
394 event of infusion site failure), the study team will be instructed to turn off closed-loop mode for  
395 approximately four hours.

396 The participant will also be asked to alert the study staff for technical issues with the Tandem  
397 research pump and/or the DiAs system, including component disconnections.

398 A glucagon emergency kit will be available at the hotel once the investigational system is in place.

399 Glycemic Treatment Guidelines will be available for staff use during the study sessions.

### 400 **6.2 Session Check-In**

401 Participants will arrive at the hotel around 4PM, approximately 2 hours before dinner. The study  
402 team will perform vital signs and inquire about any changes to the participant's medical history.  
403 Any changes to medical history will be communicated to the medical physician to ensure  
404 continued eligibility and participation.

## CLINICAL PROTOCOL

405 A urine pregnancy test will be collected for female participants of childbearing age. The test must  
406 be negative for the participant to continue with the study.

407 The subject's CGM reading, and ketone concentration will be recorded. In the event that the  
408 participant's CGM reading is not between 80-250 mg/dL or ketone concentration is  $>0.6$  mmol/L  
409 prior to initiation of DiAs, the study physician may recommend additional insulin dosing according  
410 to the participants' usual doses or glycemic treatments prior to initiating DiAs. Study physician  
411 may elect to cancel participant's participation in the hotel session if concerned about their medical  
412 safety. This participant will not be replaced but could be rescheduled for a later hotel session per  
413 investigator determination in the event of a modifiable factor that occurs early in the hotel session  
414 (e.g. severe migraine at the start of the hotel session).

415 The participant's CIQ will be discontinued, and the DiAs will be initiated. The study team will  
416 ensure the proper function of the CGM and insulin pump.

417 The CGM used in the study is FDA-approved for the non-adjunctive measurement of blood  
418 glucose (i.e. the CGM reading can be used for insulin dosing decisions). The CGM readings will  
419 be the primary source of blood glucose values. There are no protocol fingerstick blood glucose  
420 measurements other than at times of CGM calibration (if necessary) and if directed by the study  
421 team. Fingerstick blood glucose measurements may be taken whenever participants experience  
422 symptoms, if the CGM glucose is suspected to be erroneous, or any time the participant would like  
423 to be reassured.

### 424 **6.3 Glycemic Treatment Guidelines during the Hotel Portion of the Study**

425 The study physician will suggest appropriate treatment if the participant's CGM is  $<80$  mg/dL or  
426  $>250$  mg/dL, or ketone test is  $>0.6$  mmol/L at the start of the hotel session prior to the initiation of  
427 DiAs. The study subject may be initiated on DiAs at the start of the hotel study once CGM is  
428 between 80-250 mg /dL and ketone concentration is  $\leq 0.6$  mmol/L. Once DiAs is initiated, if CGM  
429  $<60$  mg/dL at any time, subjects will be given approximately 8-16 grams of fast-acting rescue  
430 carbohydrates. Study team will monitor CGM rise and will consider treating again if CGM  $<80$   
431 mg/dL after approximately 15-20 minutes. Hypoglycemic treatments can occur at any time per  
432 study physician request. Glucagon will be available at the study site and will be administered in  
433 the event of loss of consciousness or seizure related to hypoglycemia.

434 The study team may request fingersticks as needed. Any fingerstick readings obtained will be  
435 addressed the same way as the CGM values.

436 Once DiAs is initiated, if CGM is  $>250$  mg/dL for more than 3 hours or  $>400$  mg/dL at any time,  
437 study physician will be notified, and ketones will be checked. If ketone concentration is  $>0.6$   
438 mmol/L, the study team will notify the study physician and check the insulin pump infusion site  
439 and correction insulin will be administered via the subject's insulin pump or subcutaneous as  
440 needed. If subcutaneous injection is administered, closed-loop control will be stopped for up to 4  
441 hours. The study team will monitor CGM changes and ketones will be checked every 60 minutes

## CLINICAL PROTOCOL

442 until ketone concentration is  $\leq 0.6$  mmol/L. Closed-loop control using DiAs will be re-initiated  
443 once the participant's CGM reading is  $< 250$  mg/dL and ketones are  $< 0.6$  mmol/L. If ketone  
444 concentration is  $> 1.0$  mmol/L with significant symptoms, the study physician will recommend the  
445 appropriate medical treatment and the participant will be withdrawn from that portion of the study  
446 (the participant may possibly reinitiate the hotel portion of the study at a later date if a reversible  
447 cause)

448 **6.4 Study Meals**

449 Participants will eat dinner and breakfast during the session, with approximately the same amount  
450 of carbohydrate, protein, and fat for Sessions 1 and 2. Snacks with carbohydrates will not be  
451 allowed unless for the treatment of low blood sugars. Non-carbohydrates snacks may be allowed  
452 throughout the protocol per investigator discretion. Study staff will assist with bolusing decisions  
453 prior to all meals.

454 **6.5 Hotel Activities**

455 Generally, the daily routine of the participant will follow their usual daily routine as close as  
456 possible. Exercise will be permitted, to the extent it is typical for the participant and feasible for  
457 study staff to remotely monitor (e.g. would not allow a run outside).

458 If the hotel sessions are sequential within the same hotel stay, then the system algorithm will be  
459 changed by study staff to the second randomized condition at approximately 1 pm on the second  
460 day and the check-in procedures in section 6.2 do not need to be repeated. The hotel activities  
461 during the second session will be the same as the first (i.e. identical timing and content of meals,  
462 identical timing of activities).

463 **6.6 Hotel Discharge**

464 Discharge will be at approximately 1 pm. Discharge criteria is CGM value between 80-250 mg/dL  
465 with stable trend and ketones  $\leq 0.6$  mmol/L. If the CGM values are above 250 mg/dL and ketone  
466 values are  $> 0.6$  mmol/L, the study team will check the insulin pump infusion site and correction  
467 insulin will be administered per study physician judgement via the subject's insulin pump. The  
468 participant will not be able to be discharged from the study until the discharge criteria are met. The  
469 participant's CIQ will be reactivated and a qualified clinical study team member (e.g. MD, NP,  
470 PA, CDCES/RN) will assess and discuss the transition back to usual care.

471 Participants will be asked to continue monitoring ketone levels for 24-48 hours after the hotel  
472 session if ketones were  $> 0.6$  mmol/L within 12 hours prior to discharge. Urine ketone supplies  
473 may be provided for this testing. All study equipment will be returned at the time of study end.

474 **6.7 Post Hotel Check-In Visit**

475 **Visit 5**

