# CLINICAL PROTOCOL

## STUDY VISITS AND PROCEDURES SCHEDULE

	Screening	Hotel Session 1			Hotel Session 2		
		Pre-Session Check-In	Hotel Session 1	Post-Session Check-In*	Pre-Session Check-In**	Hotel Session 2	Post-Session Check-In
Location	In person or Remote	Phone/ Email/ Text	Hotel/ Rental House	Phone/ Email/ Text	Phone/ Email/ Text	Hotel/ Rental House	Phone/ Email/ Text
Visit	1	2	3	4	5	6	7
Informed Consent	X						
Eligibility Assessment	X						
Medical History	X						
HbA1c	X						
Pregnancy test (if applicable)			X			X***	
Physical Exam	X						
Vital Signs (height/weight)	X		X			X***	
Demographic Survey	X						
Baseline data download (1 week of AID data)	X						
Randomization	X						
NAP / UMPC use			X			X	
Review diabetes management and AEs		X		X	X		X

\* Post-session check-in Visit 4 will not occur, if the two hotel sessions are done sequentially

\*\* Pre-session check-in Visit 5 will not occur, if the two hotel sessions are done sequentially

\*\*\* Pregnancy test and vital signs recheck will not occur during Hotel Session 2 if the two hotel sessions are done sequentially.

---

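### In a sequential stay no ketone reading is required at the switch between algorithms unless a CGM trigger is met; narrowing the check-in waiver is a cheap, minor improvement

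*Combined protocol and SAP*

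**What the plan says.** **The waiver.** In a sequential stay, section 6.5 has staff move the participant to the second algorithm at about 1 pm on the second "day and the check-in procedures in section 6.2 do not need to be repeated". The Chapter 6 introduction agrees: "If the hotel sessions are sequential, it is not required that the initial hotel" check-in procedures be repeated (the noun is garbled there, but the sense is clear).

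**What 6.2 contains.** The study "team will perform vital signs and inquire about any changes to the" participant's medical history. A pregnancy test is done where applicable, the participant's "CGM reading, and ketone concentration will be recorded", and CGM and pump function is confirmed.

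**The limits in 6.3.** The start limits (CGM 80-250 mg/dL, ketones no higher than 0.6 mmol/L) apply "at the start of the hotel session prior to the initiation of" DiAs. Once DiAs is running, ketones are checked if CGM exceeds 250 mg/dL for more than 3 hours or exceeds 400 mg/dL at any time. If closed loop has been stopped under these rules, it restarts only with ketones below 0.6 mmol/L.

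**Discharge.** Section 6.6 requires ketones of 0.6 mmol/L or lower at discharge, at about 1 pm.

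**The visit schedule.** One footnote says: "Pregnancy test and vital signs recheck will not occur during Hotel Session 2 if the two hotel sessions are done sequentially". Two others remove the contacts at which adverse events are reviewed: "Post-session check-in Visit 4 will not occur, if the two hotel sessions are done sequentially" and "Pre-session check-in Visit 5 will not occur, if the two hotel sessions are done sequentially".

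**The concern.** The protocol asks for a ketone value when DiAs is started, when closed loop is restarted after a stop under 6.3, and at discharge. The switch between NAP and UMPC is the one transition that separates the two devices under test, and it has no such requirement.

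The trial is a safety and feasibility pilot. Section 10.2.2 lists a blood ketone level of 1.0 mmol/L or higher at any time among its reportable criteria, and section 10.3 judges relatedness partly by the timing of onset. If ketones are first found raised at final discharge, no required reading shows whether the rise began on the first or the second algorithm. The second algorithm can also be started without the ketone condition that applied to the first. With a goal of 15 completers, one event that cannot be assigned to an algorithm would be awkward in a safety summary.

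A separate and smaller matter is that nothing prompts staff to close out adverse events and device issues for the first algorithm before the second begins.

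**Working it through.** The plan gives no figure of its own on this point. The check sets the sections side by side and counts clock time.

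**Inputs.** Arrival is at about 4 pm, with dinner about 2 hours later (6.2), so the start reading and DiAs start fall between 4 pm and 6 pm on day 1. The switch is at about 1 pm on day 2 (6.5). Discharge is at about 1 pm (6.6), which in a sequential stay is taken to be day 3. The primary outcome window opens at 6 PM (Protocol Summary).

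**Step 1: time between required ketone readings, trigger not met.**
- First algorithm: 4-6 pm day 1 to 1 pm day 2 = 19 to 21 h.
- Second algorithm: 1 pm day 2 to 1 pm day 3 = 24 h.
- Check-in to discharge: 19 + 24 = 43 h to 21 + 24 = 45 h.

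**Step 2: count of required readings.**

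| | Separate stays | Sequential stay | Sequential stay, after the fix |
|---|---|---|---|
| Check-in readings | 2 | 1 | 1 |
| Switch reading | not applicable | 0 | 1 |
| Discharge readings | 2 | 1 | 1 |
| Total | 4 | 2 | 3 |
| Algorithms with both a start and an end reading | 2 of 2 | 0 of 2 | 2 of 2 |
| Longest gap within a stay | 19-21 h | 43-45 h | 24 h |

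**Step 3: does another rule fill the gap?** The 6.6 criterion applies at discharge, which follows the second algorithm. The 6.3 start limits are worded for initiating DiAs, which is already running at the switch. The 6.3 running trigger does continue across the switch, but it depends on CGM alone, so raised ketones with CGM below 250 mg/dL prompt no test.

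For example, suppose CGM is above 250 mg/dL from 10:30 am to 1 pm on day 2 and then falls. That is 2.5 h, short of the 3 h trigger, so the next required ketone reading is 24 h later. If CGM stays high past 1:30 pm, the trigger is met, but the test is then taken on the second algorithm for an excursion that ran 2.5 h on the first.

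**Step 4: is the narrower waiver safe for the items it keeps?** Section 8.2 requires a pregnancy test within 24 h before the experimental algorithms are initiated. From 4 pm to 1 pm is 21 h, so the check-in test still qualifies. Not repeating it, or the vital signs, raises no difficulty.

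**Step 5: adverse-event review.** Section 6.2 has a medical-history question but no adverse-event review. The schedule places that review at Visits 2, 4, 5 and 7, and the footnotes remove Visits 4 and 5. This is therefore a separate gap from the ketone one, with a different source in the text.

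**The case against.** The strongest reply is that 6.2 is written for arrival. The participant comes from unsupervised home use, Control-IQ is stopped and DiAs is started. None of this happens at the switch. By then the participant has had about 20 hours with at least two staff on site, one of them clinical, with CGM and insulin delivery monitored in real time (6.1). NAP and UMPC alter only the basal rate, and section 1.1 states that their commands agree within a small tolerance. A single reading at 1 pm would also miss ketosis that came and went overnight, as it would in separate stays. The waiver is permissive, so staff may test anyway.

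Most of this stands, and it is why the point is minor. It does not supply a ketone value, because continuous CGM does not measure ketones.

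A reader might infer that every check in 6.2 is lost at the switch. The documents do not support that. CGM and device status are watched continuously, the schedule itself drops the pregnancy test and vital signs, and a history question adds little after a supervised night. What is really missing is the ketone reading.

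A reader might also infer a lapse in adverse-event surveillance. The first scheduled contact after the first algorithm ends moves from 24-48 h (Visit 4) to 48-72 h (Visit 7, which is 24-48 h after discharge on day 3). That comparison counts appointments only. Visit 4 is a phone, email or text contact for someone already at home, whereas a sequential participant spends the same first 24 h under on-site clinical staff. Section 10.2.2 requires reportable events to be recorded however they come to light.

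**Conclusion.** The point holds as a minor, cheap improvement. In a sequential stay where the 6.3 trigger is not met, required ketone readings are about 43 to 45 h apart and neither algorithm has both a start and an end value. Separately, no adverse-event or device review is scheduled at the switch.

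This rests on four assumptions: DiAs starts between 4 pm and 6 pm, final discharge is at about 1 pm on day 3, staff use the waiver as written, and the 6.3 start limits are not read as applying to a change of algorithm on a running system. The last is the natural reading, but the text does not settle it. The documents give no rate of ketosis below the CGM trigger and no number of sequential stays, which could be anything from 0 to 15 completers. The expected number of affected participants therefore cannot be stated.

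Two stronger readings should be resisted. The schedule footnote and section 6.5 do not contradict each other: the schedule has no ketone row, so they differ only in scope. And nothing here shows an effect on the time-in-range comparison or on the success criteria in 12.4. The issue is safety at the switch and the attribution of events to an algorithm.

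**What to change.** 1. In 6.5 and the Chapter 6 introduction, limit the waiver to the pregnancy test and vital signs, as the schedule footnote does.
2. Require staff to record ketones and the current CGM value immediately before the second algorithm is activated.
3. If ketones exceed 0.6 mmol/L, treat under 6.3 and delay the switch until they are 0.6 mmol/L or lower. If only CGM is out of range, follow the thresholds already in force on DiAs and physician judgement. Re-applying the 80-250 mg/dL start limits to someone already on the system is not needed.
4. Add a separate line to 6.5 and to the schedule for logging adverse events and device issues on the first algorithm at the switch. Step 1 alone does not achieve this, because 6.2 contains no such review, and the 6.3 trigger leads only to physician notification and a ketone check.

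**Cost.** A short text amendment, plus one ketone strip and a few minutes of staff already present per sequential participant (at most 15 strips across completers). There will be an occasional delay. From 1 pm to the 6 PM outcome window is 5 h, which absorbs most delays. A subcutaneous correction stops closed loop for up to 4 h, so one given at 1 pm leaves 5 - 4 = about 1 h before the window opens.

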## CLINICAL PROTOCOL

476    Approximately 24-48 hours after the hotel session, the study team will contact the participant via phone/email/text to assess adverse events, adverse device effects, and device issues.

477

### 478 **Chapter 7 Medical Monitor Review**

479 The Medical Monitor will review compiled safety data at the conclusion of the trial. In addition,  
480 the Medical Monitor will review all DKA and severe hypoglycemia irrespective of relatedness to  
481 study device use, and all serious events (including UADEs) related to study device use as soon as  
482 possible to the time of occurrence. The Medical Monitor also will be informed of any ADEs not  
483 meeting criteria for a UADE if the Study PI requests the Medical Monitor review. The Medical  
484 Monitor can request modifications to the study protocol or suspension or stoppage of the study if  
485 deemed necessary based on the totality of safety data available. Details regarding the Medical  
486 Monitor review will be documented in a separate document.

## 487 **Chapter 8 Testing Procedures**

### 488 **8.1 HbA1c**

489 A blood sample will be obtained to obtain a baseline hemoglobin A1c level by the start of the hotel  
490 visit. A blood test obtained within 2 weeks prior to enrollment may be used.

491 HbA1c level may be measured by study team using the DCA2000, or another comparable point of  
492 care device, at time of screening or by the start of the hotel visit.

493 Labs may be obtained at a local laboratory (e.g. LabCorp) convenient to the participant.

### 494 **8.2 Pregnancy Test**

495 A urine pregnancy test will be required for women of childbearing potential within 24 hours prior  
496 to initiating the experimental algorithms during the hotel stay. Test must be negative to continue  
497 participation in the study.

## CLINICAL PROTOCOL

### 498 **Chapter 9 Risks Associated with Clinical Trial**

#### 499 **9.1 Potential Risks and Benefits**

500 Risks and Benefits are detailed below. Loss of confidentiality is a potential risk; however, data are  
501 handled to minimize this risk. Hypoglycemia, hyperglycemia, and ketone formation are always a  
502 risk in participants with type 1 diabetes and participants will be monitored for these symptoms.

#### 503 **9.1.1 Venipuncture Risks**

504 A hollow needle/plastic tube may be placed in the arm for taking blood samples (e.g. external  
505 HbA1c measurements for inclusion criteria). Blood draws can cause some common reactions like  
506 pain, bruising, or redness at the sampling site. Less common reactions include bleeding, formation  
507 of a small blood clot or swelling of the vein and surrounding tissues, and fainting.

